6.4. Study Treatment Compliance

When subjects are dosed, they will receive the study drug directly from the Investigator or designee, under medical supervision. The date and time of each dose administered will be recorded in the source documents and recorded in the case report form (CRF). The dose of study intervention and study subject identification will be confirmed at the time of study drug preparation by a member of the unblinded study site staff.

6.5. Concomitant Therapy

Any medication or vaccine (including over-the-counter or prescription medicines, vitamins, and/or herbal supplements, or other specific categories of interest) that the subject is receiving at the time of screening or receives during the study must be recorded along with:

- Reason for use
- Dates of administration, including start and end dates
- Dosage information, including dose and frequency

The Medical Monitor should be contacted if there are any questions regarding concomitant or prior therapy.

6.5.1. Prohibited Medications

The following medications are not allowed during the study (unless otherwise noted):

- Systemic or intestinal immune suppressants, including steroids. Inhaled or nasal steroids for respiratory diseases such as asthma and allergic rhinitis as well as topical steroids (except intestinal) are permitted.
- Oral pharmaceutical presentations (e.g., capsules) of probiotic supplements. Probiotics in foods (e.g., yogurt) are acceptable.
- Chronic or continuous oral and IV antibiotics (>2 weeks use). Topical antibiotic use is allowed.
- Systemic antiviral medications
- Systemic antifungal medications
- Live vaccines (within 14 days before Visit 3)
- Investigational drugs or devices

Note: After screening, use of any of these medications may be permitted if they are required for treatment of an AE, if the Investigator believes it is necessary. The use of any of these medications should be documented as a protocol deviation, even if they are used to treat AEs. The Investigator should inform the Medical Monitor of such use as early as possible.

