PRV-015, a fully human immunoglobulin (IgG1κ) mAb, binds to and inhibits the function of IL-15 in all of its presentations (cis, trans, soluble IL-15 bound to IL-15R α), and blocks IL-15-induced T-cell proliferation (Villadsen 2003). It has also demonstrated dose-dependent inhibition of IL-15-induced tumor necrosis factor alpha (TNF- α) production. Thus, PRV-015 is a plausible candidate for the treatment of celiac disease.

PRV-015 was previously tested in clinical trials for efficacy and safety in patients with rheumatoid arthritis (RA) (Baslund 2005, McInnes 2006), refractory celiac disease Type II (RCD-II) (Cellier 2019), and psoriasis (Lebrec 2013) and has shown acceptable safety and tolerability in all studies. Proof of concept was achieved in RA and RCD-II, while PRV-015 showed no efficacy in psoriasis.

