5.2. Exclusion Criteria

Subjects are excluded from the study if any of the following criteria applies at either screening or, if applicable, at randomization (Visit 3):

1. Current diagnosis of any severe complication of celiac disease, such as RCD-I or RCD-II, enteropathy-associated T-cell lymphoma (EATL), ulcerative jejunitis, or GI perforation.
2. Diagnosis of any chronic, active GI disease other than celiac disease, such as active, untreated peptic ulcer, eosinophilic esophagitis, erosive esophagitis, ulcerative colitis or Crohn's disease, microscopic colitis, irritable bowel syndrome, small intestinal bacterial overgrowth, tropical sprue, or other GI and non-GI disorder or prior GI surgery that may, in the Investigator's opinion, interfere with the assessment of symptoms of abdominal pain, diarrhea, or other components of celiac disease.
3. Any known, symptomatic food allergy that, in the opinion of the Investigator, may interfere with the conduct or interpretation of the study.
4. Presence of any of the following related to infection:
 - a. Active acute infection with flu-like symptoms such as fever, cough, or shortness of breath; or active infections requiring systemic (intravenous or intramuscular) treatment (antibiotics, antifungal, or antiviral).
 - b. Active GI infection, including *H. pylori*.
 - c. History of tuberculosis (TB) except for successful chemoprophylaxis for positive TB tests.
 - d. Positive Interferon Gamma Release Assay (IGRA) test at screening. Subjects with potential false-positive tests may have the test repeated. If chest X-ray is also clear, they may be enrolled.

- e. History of an opportunistic infection typical of those seen in immunocompromised patients (e.g., herpes zoster, systemic candida infection, or systemic fungal infection) within 3 years prior to screening.
5. Any of the following laboratory test abnormalities at screening or Visit 1 (Day -28):
 - a. Alanine aminotransferase (ALT) and aspartate aminotransferase (AST) >3 times the upper limit of normal (ULN).
 - b. Hemoglobin <9 g/dL (<90 g/L in SI units).
 - c. Platelet count <100,000 mm³ (<100/L).
 - d. White blood cell count <3,000 cells/mm³ (<3.0 ×10⁹/L).
 - e. Creatinine >1.5 mg/dL.
 - f. Hemoglobin A1c (HbA1c) >9% (>90 mmol/mol) in subjects with a concurrent diagnosis of Type 1 or Type 2 diabetes.
6. Use of systemic immune suppressants (including systemic or GI topical steroids) during the screening or single-blind placebo run-in period.

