7. Required use of a prohibited medication (see Section 6.5.1) during the screening or single-blind placebo run-in period.
8. Current diagnosis or recent history of cancer within the past 5 years, except successfully treated basal cell or squamous cell carcinoma, cervical carcinoma-in-situ, or early-stage prostate cancer.
9. Known or suspected exposure to COVID-19 infection in the 4 weeks before screening.
10. Administration of a live vaccine within 14 days prior to randomization and the first administration of study drug at Visit 3.
11. History or presence of any clinically significant disease that, in the opinion of the Investigator, may confound the subject's participation and follow-up in the clinical trial or put the subject at unnecessary risk, including but not limited to: uncontrolled hypertension (BP ≥180/110 mm/Hg), unstable angina, Class II congestive heart failure or major fluid overload, coronary angioplasty or myocardial infarction within the past 6 months, clinically significant arrhythmias or electrocardiogram (ECG) abnormalities, severe chronic pulmonary disease, or any renal, hematologic, GI, immunologic, dermatologic, neurologic, or psychiatric disease.
12. History of significant substance or alcohol abuse during the 12 months prior to screening as obtained by medical record and/or subject report.
13. Hepatitis B virus (HBV), hepatitis C virus (HCV), or human immunodeficiency virus (HIV) positive test results.
14. Females who are pregnant or planning to become pregnant during the study period, or who are currently breastfeeding.
15. Participation in another investigational drug or device study or treatment with an investigational drug within 30 days or 5 half-lives, whichever is longer, prior to screening.
16. Any other reason that, in the opinion of the Investigator, may prevent the subject from safely participating in the study or complying with protocol requirements, including the endoscopies and biopsies.

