7.1. Discontinuation of Study Treatment

In rare instances, it may be necessary for a subject to permanently discontinue (definitive discontinuation) study treatment. If a subject discontinues study drug administration after randomization (Visit 3), the subject will be encouraged to return for all subsequent on-site visits as listed in the SoA (i.e., Visits 4, 5, 7, 9, 11, 13, 14, 15, and 16). If the discontinued subject chooses to not return for on-site visits, study personnel should make every effort to conduct the Early Termination (ET) visit and ask the subject to return 6 weeks after the last dose of the study drug for the final safety follow-up visit (see Section 1.3). If a subject discontinues study drug administration before randomization, no further assessments will be conducted.

The reasons for permanent discontinuation of study treatment at any time during the study include but are not limited to the following:

- Safety reasons, either at the discretion of the Investigator or at the subject's request.
 - In particular, subjects can be discontinued from study treatment if they develop severe complications of celiac disease that require intensive treatment (e.g., RCD-I or RCD-II, jejunitis, perforation).
 - Malignancy
 - Active TB
 - A serious opportunistic infection
 - Pregnancy (female subjects)
 - Anaphylaxis or severe hypersensitivity reactions after the initial injection(s)
- Significant protocol violations (e.g., noncompliance with study procedures), at the discretion of the Sponsor
- The use of prohibited therapy that may interfere with the study assessment and analysis (Section 6.5.1). The Investigator is required to report all such information on the CRF and decide, upon discussion with the Sponsor, whether the subject is to be discontinued from study treatment.

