8.4.7. Adverse Events of Special Interest

The treatment-emergent AESIs to be collected are severe opportunistic infections and hypersensitivity reactions of at least moderate severity.

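### Protocol 6.5.1 restricts live vaccines only before Visit 3, so as worded no rule covers them during dosing or follow-up (Day 1 to Day 197)

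*Protocol*

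**What the plan says.** Protocol 6.5.1 opens its list with "The following medications are not allowed during the study (unless otherwise noted"). The vaccine item carries its own limit: "Live vaccines (within 14 days before Visit 3"). The note below the list adds: "The use of any of these medications should be documented as a protocol deviation, even if they are used to treat AEs".

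Exclusion 10 in Protocol 5.2 sets the same limit for entry: "Administration of a live vaccine within 14 days prior to randomization and the first administration of study drug at Visit 3".

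Protocol 6.5 requires every medication or vaccine to be recorded with its dates, and names the Medical Monitor as the contact for questions. It bars nothing.

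On the drug and the risks the protocol watches for:

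- Section 2.2 says that PRV-015 "blocks IL-15-induced T-cell proliferation".
- Exclusion 4e covers, within 3 years before screening, "History of an opportunistic infection typical of those seen in immunocompromised patients".
- Section 7.1 lists among the reasons to stop treatment "A serious opportunistic infection".
- Section 8.4.7 defines the events of special interest as "severe opportunistic infections and hypersensitivity reactions of at least moderate severity".

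SAP 8.6.1.1 carries the vaccine item, with its pre-Visit-3 window, into the list it uses to count prohibited medication taken after randomization.

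**The concern.** The protocol is careful about live vaccines in the fortnight before the first double-blind dose, then says nothing while the antibody is given and followed up. A site that applies 6.5.1 exactly could give a licensed live vaccine between two doses without breaching a rule, and would have no deviation to log.

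What is at stake is mainly subject safety. A protocol that excludes recent opportunistic infection, stops treatment for a serious one and tracks severe ones would be expected to say what happens with live vaccines on treatment. Consistency between sites is a lesser matter: some may assume a ban that the text does not contain, others may not.

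**Working it through.** **Inputs.** From the Schedule of Activities (Protocol 1.3): Visit 3 = Day 1, Visit 14 (last dose) = Day 155, Visit 16 = Day 197 with a window of ±7 days. From Protocol 9.2: about 220 subjects, randomized 1:1:1:1.

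**The plan's own figure.** Protocol 4.1 puts Visit 16 six weeks after the last planned dose. 197 − 155 = 42 days, and 42 / 7 = 6 weeks. This reproduces.

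**Length of the uncovered period.**

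- First to last planned dose: 155 − 1 = 154 days.
- Last dose to Visit 16: 42 days.
- Total: 154 + 42 = 196 days, or 28 weeks.
- Visit 16 at the ends of its window (Day 190 or Day 204): 190 − 1 = 189 to 204 − 1 = 203 days.

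**Overlap with the restriction.** The restricted 14 days end before Day 1, so they share 0 days with this period. Doses are given at Visits 3 to 14, which is 14 − 3 + 1 = 12 doses; 0 of the 12 fall inside the restricted window.

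**Subjects on active drug.** 3/4 × 220 = 165.

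**The list, item by item.** 6.5.1 has seven items: immune suppressants, oral probiotic supplements, prolonged antibiotics, systemic antivirals, systemic antifungals, live vaccines, and investigational drugs or devices. Six apply during the study. Only the vaccine item ends before double-blind treatment starts.

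**Search for another rule.** Protocol 5.3 (lifestyle), 6.5 (recording), 6.6 (dose modification) and 7.1 (discontinuation) contain no live-vaccine restriction. The investigational-products item does not reach a licensed vaccine. The deviation note in 6.5.1 attaches to the listed medications as worded, so it does not reach a vaccine given from Visit 3 on.

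**The SAP bullet.** The SAP 8.6.1.1 tabulation counts use after randomization, while the vaccine window closes at Visit 3. An entry could arise only if Visit 3 dosing was rescheduled after randomization, which SAP 8.6.1.5 says happened in some cases. Even then the vaccine would come before treatment initiation, and so would fall outside the SAP's own definition of an intercurrent event. The bullet does no work.

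**The case against.** Five points can be made against this.

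1. **The lead sentence might be read as a study-wide ban, with the bracket adding a washout.** That may have been the intent. The wording does not say it: the lead sentence yields to whatever an item notes otherwise, and the duration bracket in the antibiotics item also narrows that item. If a full ban was meant, the line still needs rewording.

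2. **No harm is documented.** This stands. Neither document says that live vaccines are unsafe with PRV-015. The benefit/risk summary (Protocol 2.3) lists mild and transient reactions and refers to the Investigator Brochure, which is not available here. The infection provisions do not mention vaccines. The link is an inference from mechanism and from the protocol's own vigilance.

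3. **There are partial safeguards.** Vaccines are recorded, the Medical Monitor can be asked, treatment can be stopped for safety, and the DMC meets at least quarterly. All true, but none is a restriction.

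4. **Extending the ban has side effects.** This stands and shapes the fix. SAP 8.1.5 names prohibited medication as a possible major violation, so vaccinated subjects could drop out of the per-protocol set. Protocol 7.1 allows prohibited therapy to lead to a discontinuation discussion. The exception in the 6.5.1 note is for treating an adverse event, which does not fit a preventive vaccine.

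5. **It may be too late.** SAP 8.9 describes the DMC's work in the past tense, and SAP 8.6.1.5 does the same for visit delays and missed diary entries. This suggests, without proving, that conduct was largely over.

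**Conclusion.** The gap in coverage is real on the text. From Day 1 to Day 197, nominally 196 days and 12 planned doses, no rule bars a licensed live vaccine or makes it a deviation. It is a cheap, safety-directed improvement and not a flaw in the analysis. The day counts and the figure of 165 subjects describe planned exposure, not risk; the number of subjects vaccinated is not given.

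A reader might infer more, in three directions that the documents do not support:

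- **That 6.5.1 contradicts itself.** It does not. Its lead sentence allows an item to note a different scope, and the vaccine item does so.
- **That live vaccines are known to be dangerous with this drug.** Nothing in either document says so, and the size of any hazard cannot be judged from them.
- **That the primary result is biased, or that intercurrent events are miscounted in a way that matters.** The primary estimand follows a treatment-policy strategy, so all collected scores are used. No effect of a vaccine on abdominal symptoms is claimed, and the SAP bullet copies the protocol faithfully.

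The conclusion assumes that the visible text is the whole rule and that the Investigator Brochure or site manuals, which are not available here, add no separate restriction.

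**What to change.** **If dosing is ongoing:**

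- Amend the 6.5.1 item so that live vaccines are prohibited from 14 days before Visit 3 through Visit 16. Leave Exclusion 10 as it is. Visit 16 is a practical endpoint: the documents give no washout basis for it, and the contraception precautions run to 3 months after the last dose.
- State in SAP 8.1.5 that a live vaccine alone is not a major violation for the per-protocol set.
- Remove the live-vaccine bullet from the SAP 8.6.1.1 list instead of extending it. The list serves events that may interfere with the primary endpoint, and no such interference is claimed for a vaccine. With the bullet gone, the sensitivity analysis in SAP 8.6.1.4 needs no exception to keep later symptom scores from being set to missing. On-study vaccines still appear in the concomitant-medication listing under SAP 8.5.

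**Cost.** One protocol line, but by amendment, which needs IRB/IEC approval (Protocol 10.1.1) and re-consent if the consent form changes (10.1.3). Two small SAP edits. A few vaccinations would be deferred, and some logged deviations could prompt a discontinuation discussion under 7.1. No new data are needed, because 6.5 already requires vaccines to be recorded with dates.

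**If dosing has ended:** no protocol change is useful. Permitted vaccines should not be relabelled as prohibited after the fact, and the existing listing already shows any that were recorded.

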6.6. Dose Modification

Subjects should receive the dose regimen as assigned through randomization. No dose modification during the double-blind treatment period is allowed. Patients who meet the criteria for study treatment discontinuation should follow the instructions in Section [7.1](#).

6.7. Treatment after the End of the Study

None.

7. Discontinuation of Study Treatment and Subject Discontinuation/Withdrawal

Discontinuation of study treatment or withdrawal from the study will be noted in the subject's record.

7.1. Discontinuation of Study Treatment

In rare instances, it may be necessary for a subject to permanently discontinue (definitive discontinuation) study treatment. If a subject discontinues study drug administration after randomization (Visit 3), the subject will be encouraged to return for all subsequent on-site visits as listed in the SoA (i.e., Visits 4, 5, 7, 9, 11, 13, 14, 15, and 16). If the discontinued subject chooses to not return for on-site visits, study personnel should make every effort to conduct the Early Termination (ET) visit and ask the subject to return 6 weeks after the last dose of the study drug for the final safety follow-up visit (see Section 1.3). If a subject discontinues study drug administration before randomization, no further assessments will be conducted.

The reasons for permanent discontinuation of study treatment at any time during the study include but are not limited to the following:

- Safety reasons, either at the discretion of the Investigator or at the subject's request.
 - In particular, subjects can be discontinued from study treatment if they develop severe complications of celiac disease that require intensive treatment (e.g., RCD-I or RCD-II, jejunitis, perforation).
 - Malignancy
 - Active TB
 - A serious opportunistic infection
 - Pregnancy (female subjects)
 - Anaphylaxis or severe hypersensitivity reactions after the initial injection(s)
- Significant protocol violations (e.g., noncompliance with study procedures), at the discretion of the Sponsor
- The use of prohibited therapy that may interfere with the study assessment and analysis (Section 6.5.1). The Investigator is required to report all such information on the CRF and decide, upon discussion with the Sponsor, whether the subject is to be discontinued from study treatment.

7.1.1. Emergency Data Monitoring Committee Meeting

The DMC will hold an emergency meeting if any of the following occur:

- Death of a subject
- Anaphylactic reaction in any subject
- A life-threatening AE in any subject that is considered by the investigator to be possibly related to study drug

The DMC would review unblinded safety information to determine whether any change in study conduct should occur.

7.2. Subject Withdrawal from the Study

A subject may withdraw from the study at any time at his/her own request. If possible, the early termination assessments listed for Visit 15 (Week 24) in the SoA (Section 1.3) should be conducted before the withdrawal, including EGD with biopsy, unless the withdrawal occurs before randomization.

A subject who withdraws consent from the study will be permanently discontinued both from the study drug and from any further assessments.

If the subject withdraws consent for disclosure of future information, the sponsor may retain and continue to use any data collected before such a withdrawal of consent.

If a subject withdraws from the study, he/she may request destruction of any samples taken and not yet tested, and the Investigator must document this in the site study records.

7.3. Lost to Follow-up

A subject will be considered lost to follow-up if he or she repeatedly fails to return for scheduled visits and is unable to be contacted by the study site. The site should attempt to contact the subject at least 3 times and document all such attempts before determining the subject has been lost to follow-up.

8. Study Assessments and Procedures

8.1. All Laboratory Tests

The maximum amount of blood collected from each subject over the duration of the study is expected not to exceed 400 mL over a period of approximately 9 months. This estimation does not include repeat or unscheduled samples, which may be taken for safety reasons or for technical issues with collected samples.

All laboratory tests to be conducted at in-office visits are listed as follows.

Screening Visit (within 28 days before Visit 1)

- Chemistry: calcium, ALT, AST, albumin, total and direct bilirubin, sodium, potassium, blood urea nitrogen (BUN), creatinine, chloride, CO₂, glucose, total protein, alkaline phosphatase (ALP) (if ALP is >3 x ULN, test 5' nucleotidase or GGT), magnesium, phosphorus
- Complete blood count (CBC): hemoglobin, hematocrit, platelets, white blood cell count (WBC) with differential, red blood cell count (RBC), mean corpuscular volume (MCV), mean corpuscular hemoglobin concentration (MCHC), mean cell hemoglobin (MCH)
- Urinalysis (dipstick and microscopic)
- HbA1C (subjects with diagnosed Type 1 or Type 2 diabetes only)
- HLA DQ2/8 (as needed)
- Testing for HIV, HBV and HCV for exclusion as follows:
 - HIV: positive antibody to p24 antigen (Ab-p24Ag) for human immunodeficiency virus (HIV) 1 or 2 confirmed by positive HIV 1/2 Western blot
 - HBV: HBsAg, anti-HBc total (IgM and IgG) confirmed by positive HBV DNA, anti-HBs
 - HCV: HCV antibody confirmed by positive HCV RNA
- IGRA
- *H. pylori* stool test
- Serum pregnancy test (all WOCBP only)
- FSH/LH for women with suspected menopause (i.e., not surgical menopause)
- Serum IgA
- Anti-tTG IgA and IgG, anti-DGP IgA and IgG

Visit 1 (Single-blind run-in Week -4)

- Chemistry (same tests as screening)
- CBC (same tests as screening)
- HbA1C (subjects with diagnosed Type 1 or Type 2 diabetes only)
- Urinalysis (same tests as screening)
- Stool and urine gluten tests
- Urine pregnancy (WOCBP only)

Visit 2 (Single-blind run-in Week -2)

- Stool and urine gluten tests

- Urine pregnancy (WOCBP only)

Visit 3 (Week 0/Day 1)

- Chemistry (same tests as screening)
- CBC (same tests as screening)
- Urinalysis (same tests as screening)
- Stool and urine gluten tests
- Urine pregnancy test (WOCBP only)
- Anti-tTG IgA, anti-DGP IgA
- Ferritin, iron, TIBC, vitamins D, B12, folate
- Serum biomarkers (e.g., IL-15)
- Trough concentration of PRV-015
- ADA

Visit 4 (Week 2/Day 15)

- Stool and urine gluten tests
- Trough concentration of PRV-015
- ADA

Visit 5 (Week 4/Day 29)

- Chemistry (same tests as screening)
- CBC (same tests as screening)
- HbA1C (subjects with diagnosed Type 1 or Type 2 diabetes only)
- Urinalysis (same tests as screening)
- Stool and urine gluten tests
- Urine pregnancy test (WOCBP only)
- Anti-tTG IgA, anti-DGP IgA
- Serum biomarkers (e.g., IL-15)
- Trough concentration of PRV-015
- ADA

Visit 7 (Week 8/Day 57)

- Chemistry (same tests as screening)
- CBC (same tests as screening)
- Urinalysis (same tests as screening)
- HbA1C (subjects with diagnosed Type 1 or Type 2 diabetes only)
- Stool and urine gluten tests
- Urine pregnancy test (WOCBP only)
- Anti-tTG IgA, anti-DGP IgA
- Serum biomarkers (e.g., IL-15)
- Trough concentration of PRV-015

Visit 9 (Week 12/Day 85)

- Chemistry (same tests as screening)

- CBC (same tests as screening)
- HbA1C (subjects with diagnosed Type 1 or Type 2 diabetes only)
- Urinalysis (same tests as screening)
- Stool and urine gluten tests
- Urine pregnancy test (WOCBP only)
- Anti-tTG IgA, anti-DGP IgA
- Ferritin, iron, TIBC, vitamins D, B12, folate
- Serum biomarkers (e.g., IL-15)
- Trough concentration of PRV-015
- ADA

Visit 11 (Week 16/Day 113)

- Chemistry (same tests as screening)
- CBC (same tests as screening)
- HbA1C (subjects with diagnosed Type 1 or Type 2 diabetes only)
- Urinalysis (same tests as screening)
- Stool and urine gluten tests
- Urine pregnancy test (WOCBP only)
- Anti-tTG IgA, anti-DGP IgA
- Serum biomarkers (e.g., IL-15)
- Trough concentration of PRV-015

Visit 13 (Week 20/Day 141)

- Chemistry (same tests as screening)
- CBC (same tests as screening)
- HbA1C (subjects with diagnosed Type 1 or Type 2 diabetes only)
- Urinalysis (same tests as screening)
- Stool and urine gluten tests
- Urine pregnancy test (WOCBP only)
- Anti-tTG IgA, anti-DGP IgA
- Serum biomarkers (e.g., IL-15)
- Trough concentration of PRV-015

Visit 14 (Week 22/Day 155)

- Trough concentration of PRV-015
- ADA

Visit 15 (Week 24/Day 169) or Early Termination

- Chemistry (same tests as screening)
- CBC (same tests as screening)
- HbA1C (subjects with diagnosed Type 1 or Type 2 diabetes only)
- Urinalysis (same tests as screening)
- Stool and urine gluten tests

- Urine pregnancy test (WOCBP only)
- Anti-tTG IgA, anti-DGP IgA
- Ferritin, iron, TIBC, vitamins D, B12, folate
- Serum biomarkers (e.g., IL-15)
- Trough concentration of PRV-015
- ADA

Visit 16 (Week 28/Day 197)

- Chemistry (same tests as screening)
- CBC (same tests as screening)
- HbA1C (subjects with diagnosed Type 1 or Type 2 diabetes only)
- Urinalysis (same tests as screening)
- Stool and urine gluten tests
- Urine pregnancy test (WOCBP only)
- Anti-tTG IgA, anti-DGP IgA
- Serum biomarkers (e.g., IL-15)
- Trough concentration of PRV-015
- ADA

